8.3.2 Laboratory evaluations

In the case where a laboratory range is not specified by the protocol, but is outside the reference range for the center or study central laboratory assays at screening, a decision regarding whether the result is of clinical significance or not shall be made by the Investigator and shall be based, in part, upon the nature and degree of the observed abnormality. The assessment may be repeated once (for the purpose of inclusion) and in any case, prior to enrollment/randomization, to rule out laboratory error.

In all cases, the Investigator must document in the source documents, the clinical considerations (*i.e.*, result was/was not clinically significant and/or medically relevant) in allowing or disallowing the subject to continue in the study. Clinically relevant deviations of laboratory test results occurring during or at completion of the study must be reported and discussed with Novartis personnel. The results should be evaluated for criteria defining an adverse event and reported as such if the criteria are met. Repeated evaluations are mandatory until normalization of the result(s) or until the change is no longer clinically relevant. In case of doubt, Novartis personnel should again be contacted.

For off-site visits (described in [Section 3.1](#)), samples will be collected, processed and shipped from the off-site location to the Central Laboratory for analysis in line with instructions contained in the study laboratory manual.

8.3.2.1 Clinical Chemistry, including coagulation parameters

Sodium, potassium, creatinine, BUN/urea, uric acid, chloride, albumin, calcium, alkaline phosphatase, total bilirubin, bicarbonate/HCO₃, LDH, GGT, AST, ALT, CK, glucose, total cholesterol, HDL-C, LDL-C, triglycerides, Prothrombin Time (PT)/ International Normalized Ratio (INR), activated partial thromboplastin time (aPTT).

If the total bilirubin concentration is increased above 1.5 times the upper limit of normal, direct and indirect reacting bilirubin should be differentiated.

HbA1c and CCI will be collected during the trial as per the Assessment Schedule ([Table 8-1](#)).

8.3.2.2 Hematology

Hemoglobin, hematocrit, red blood cell count, white blood cell count with differential, and platelet count will be measured.

8.3.2.3 Urinalysis

A midstream urine sample (approx. 30 mL) will be obtained, in order to avoid contamination with epithelial cells and sediments, and allow proper assessments. A semi-quantitative 'dipstick' evaluation for the following parameters will be performed: specific gravity, pH, glucose, protein, bilirubin, ketones, leukocytes, creatinine, and blood, microalbumin. If the dipstick result is positive for protein leucocytes and/or blood, the sample will be sent for microscopic analysis of WBC, RBC and casts.

8.3.2.4 Endocrinology

Thyroid function tests: TSH and total T4.

8.3.2.5 Viral Monitoring

CMV and EBV viral load and serology (IgM and IgG) will be obtained at screening and monthly following dosing during the treatment period. SARS-CoV-19 viral load and serology (IgM and IgG) will be obtained at screening. Serum will be banked for subsequent evaluation as needed, for clinical assessment or when testing sensitivity/specifity are better understood. This banked specimen may be analyzed for additional infectious agents if warranted.

HSV viral load and serology (IgM and IgG) will be obtained at screening and serology will be assessed at week 16, 32 and 48 following dosing. This will provide surveillance for new exposure, seroconversion, and potential reactivation of viral infections.

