Blockade of CD40 receptors by CFZ533 impairs T-lymphocyte dependent antibody responses (TDAR) to vaccines. CFZ533 plasma concentrations above CCI were associated in non-human primates with complete suppression of germinal center development, and prevented recall antibody responses after Keyhole Limpet Hemocyanin (KLH) vaccinations. Upon elimination of CFZ533 a normal memory antibody response could be mounted in all animals (more details in the Investigator Brochure). In healthy volunteers a single dose of 3 mg/kg (IV or SC) of CFZ533 transiently suppressed anti-KLH responses to the first KLH immunization at CFZ533 concentrations corresponding to full receptor occupancy (RO) in whole blood (RO; ≥90%) for about 3-4 weeks. Anti-KLH primary responses were detected in all subjects as CFZ533 concentration and accompanying receptor occupancy declined. All subjects were able to mount recall responses to a second KLH immunization (administered after loss of RO; details in the IB).

CFZ533 is non-depleting of cells that express CD40, including memory B lymphocytes, which supports rapid functional recovery of immune responses as the compound is being cleared. CFZ533 is not expected to affect plasma cells as they are not believed to express functional CD40 receptors.

The ability to mount a T lymphocyte-dependent primary and memory immune response to vaccines and pathogens is expected to be impaired in subjects with plasma CFZ533 concentrations CCI. The risk to subjects of vaccination ineffectiveness while exposed to CFZ533 is mitigated by eligibility requirements of up-to-date immunizations (per local guidelines) and confirmation of protective serology prior to initial dosing with CFZ533. Mitigation plans for the infection risks to subjects during exposure to CFZ533 was covered previously. Once CFZ533 is cleared, subjects are expected to mount normal primary and secondary immune responses to vaccines and pathogens as CD40 receptor blockade is released.

Pre-formed immunity to pathogens and vaccines (circulating antibody titers and plasma cells) is not expected to be affected by exposure to CFZ533. Plasma cells are long lived and confer long-lasting immune protection to subjects, for example at least 10 years for tetanus toxoid and potentially even longer for measles. Thus, subjects with pre-formed immunity are expected to retain protection against pathogens during exposure to CFZ533.

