10.2 Additional Safety Monitoring

10.2.1 Viral safety monitoring

Subjects are anticipated to retain immune memory for antigens to which they were previously exposed, but not mount a humoral immune response and memory for neo-antigens. Combined immunotherapy is expected to increase the risk for infection. Thus no additional immunosuppressive agents are permitted in this study.

See [Section 16.3](#) for general guidance information on CMV and EBV.

At screening, identify and exclude subjects with evidence of active CMV, EBV, HSV 1 and 2, or SARS-CoV-2 infection based on baseline viral load (determined via polymerase chain reaction (PCR)) or positive IgM serology in the absence of positive IgG.

At screening, identify subjects at risk for CMV, EBV, HSV, or SARS-CoV-2 primary infection or reactivation based on baseline IgG serology (negative or positive IgG serology, respectively). Rescreening for SARS-CoV-2 is permitted in persistently asymptomatic or post-symptomatic subjects, but study drug must be able to be administered within 100 days of diagnosis of T1DM and viral load must be negative and IgG titers positive.

During the study identify subjects with CMV or EBV reactivation or primary infections with serial PCR to detect virus DNA in addition to serology at least at monthly intervals, or when the clinical presentation suggests possible CMV or EBV infection. During the study monitor for HSV seroconversion quarterly (weeks 16, 32, and 48).

During the study, for subjects with evidence of an active CMV infection based on viral load measurement, increase the frequency of serial PCR to detect CMV DNA and clinical monitoring for early signs of CMV end organ disease, to at least weekly frequency until resolution of the viral infection. Consider consultation with an infectious disease expert.

During the study, for subjects with confirmed or probable cytomegalovirus disease, consider stopping study drug and consider initiating appropriate anti-cytomegalovirus therapy (or other anti-viral therapy as appropriate) in consultation with an infectious disease expert.

For subjects with potential infectious symptoms during the trial, but without laboratory confirmation of CMV or EBV infection, consider age- and country-appropriate infectious exposure risks for alternative infectious etiologies, consider direct isolation of pathogens,

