virology, and/or serology, and initiating appropriate targeted anti-viral or anti-bacterial therapies as indicated in consult with an infectious disease expert. Additional viral infection should be considered and viral load/ titer assessed as serology/ immunoglobulin response may be diminished.

For subjects with potential infectious COVID-19 symptoms during the trial repeat virology (PCR) to detect SARS-CoV-2 RNA, serologic evaluation, and clinical monitoring for early signs of end organ disease and initiating appropriate targeted anti-viral or anti-bacterial therapies as indicated in consult with an infectious disease expert may be warranted.

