7.1 Variables

Safety variables include adverse events, vital signs (blood pressure [SBP and DBP] and pulse), height and weight, ECG intervals, laboratory measurements (hematology, clinical chemistry, urinalysis, coagulation panel, virology and viral serology for SARS-CoV-2, CMV, EBV, and HSV), as well as subject demographics, baseline characteristics, and treatment information.

Safety summaries (tables, figures) include only data from the on-treatment period with the exception of baseline data which will also be summarized where appropriate (e.g. change from baseline summaries). In particular, summary tables for adverse events (AEs) will summarize only on-treatment events, with a start date during the on-treatment period (*treatment-emergent* AEs).

For all safety data listings (e.g. ECG, lab, vital signs, AEs), data collected during the post-treatment period will be flagged.

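### The only scheduled on-treatment HSV test is an antibody test that the protocol expects CFZ533 to weaken, so by-arm HSV seroconversion should not be read as a comparative infection rate

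*Protocol*

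**What the plan says.** **Schedule.** Protocol 8.3.2.5: "HSV viral load and serology (IgM and IgG) will be obtained at screening and serology will be assessed at week 16, 32 and 48". The stated purpose follows: "This will provide surveillance for new exposure, seroconversion, and potential reactivation of viral infections". Protocol 10.2.1 repeats the rule: "During the study monitor for HSV seroconversion quarterly (weeks 16, 32, and 48". In Table 8-1 the HSV viral load row is marked at screening only. HSV viral load and serology appear once more, in follow-up, at Week 68 or Week 72; the column cannot be settled from the extracted table. CMV and EBV, by contrast, have PCR as well as serology at least monthly during treatment (10.2.1).

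**Drug effect.** Protocol 10.2.1 expects subjects to keep existing immune memory "but not mount a humoral immune response and memory for neo-antigens". Protocol 4.5 says: "The ability to mount a T lymphocyte-dependent primary and memory immune response to vaccines and pathogens is expected to be impaired". It reports that a single 3 mg/kg dose in healthy volunteers "transiently suppressed anti-KLH responses to the first KLH immunization at CFZ533 concentrations corresponding to full receptor occupancy", with primary responses appearing as the drug cleared. On subjects with possible infectious symptoms, 10.2.1 asks for viral load or "titer assessed as serology/ immunoglobulin response may be diminished".

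**Analysis.** SAP 7.1 counts "virology and viral serology for SARS-CoV-2, CMV, EBV, and HSV" among the safety variables. SAP 7 produces safety outputs by treatment. SAP 7.1 restricts safety tables and figures to the on-treatment period plus baseline, and SAP 4.1.1 ends that period 98 days after the last dose. Later data are listed and flagged.

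**The concern.** Safety is one of the two primary objectives, and Protocol 4.5 treats infection as an important risk. A subject who is HSV IgG negative, IgM negative and without viral load at screening can enter: exclusion criterion 10 does not bar that pattern, and 10.2.1 labels IgG-negative subjects as at risk of primary infection. For such a subject on CFZ533, the only scheduled HSV marker during a year of treatment is one that the protocol expects the drug to weaken. A placebo subject with the same silent infection would be expected to seroconvert.

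Detection may therefore differ by arm for a reason unrelated to infection risk. A reader of the by-arm laboratory summaries would see fewer HSV seroconversions on CFZ533 and could take that as reassurance. Nothing in the visible SAP text warns against this.

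**Working it through.** The plan states no detection rate or infection rate for HSV, so there is no figure to reproduce.

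**Step 1. The sections side by side.** 8.3.2.5 and 10.2.1 offer on-treatment serology as evidence of new exposure. 4.5 and 10.2.1 say the response that serology measures is impaired in subjects on the drug. On the protocol's own terms the surveillance claim does not hold equally in both arms. In subjects already IgG positive at baseline, seroconversion cannot show reactivation in either arm; that gap is not arm-specific.

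**Step 2. Does the off-drug test repair the summaries?**
- Day 8 is Week 1, so Week w is Day 1 + 7w. The last dose is at Week 51 (Protocol summary, study treatment): 1 + 7 × 51 = Day 358.
- End of on-treatment period: 358 + 98 = Day 456. With the longest delay allowed in Protocol 6.1 (6 days): 358 + 6 + 98 = Day 462.
- Earliest Week 68 visit: 477 − 7 = Day 470. Week 72: 1 + 7 × 72 = Day 505.
- 470 is later than 462, so at either visit the test is post-treatment. A seroconversion that appears after washout would reach the flagged listing but no by-arm summary.

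**Step 3. Illustration of direction and possible size.** Assumptions, none of them in the documents: equal true risk in both arms, all subjects susceptible, placebo serology sensitivity 0.9, and CFZ533 sensitivity varied. Arms: 44 × 2/3 ≈ 29 and 44 × 1/3 ≈ 15.

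Observed risk ratio = true risk ratio × (sensitivity on CFZ533 ÷ sensitivity on placebo).

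Expected detections = arm size × risk × sensitivity. At an assumed 10% risk, true infections are 29 × 0.10 = 2.9 and 15 × 0.10 = 1.5, and placebo detections are 15 × 0.10 × 0.9 = 1.35.

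| Sensitivity on CFZ533 | Observed risk ratio when true ratio is 1 | Expected detections, CFZ533 | True ratio that would look like 1 |
|---|---|---|---|
| 0.9 | 0.9/0.9 = 1.00 | 29 × 0.10 × 0.9 = 2.61 | 1.0 |
| 0.5 | 0.5/0.9 = 0.56 | 29 × 0.10 × 0.5 = 1.45 | 0.9/0.5 = 1.8 |
| 0.2 | 0.2/0.9 = 0.22 | 29 × 0.10 × 0.2 = 0.58 | 0.9/0.2 = 4.5 |
| 0 | 0 | 0 | no finite value |

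At 5% risk, placebo detections are 15 × 0.05 × 0.9 = 0.68; at 20% they are 15 × 0.20 × 0.9 = 2.70. Only baseline-seronegative subjects can seroconvert, so real counts would be smaller. If the seronegative share is the same in both arms, the ratio is unchanged. Across the 5% to 20% range expected detections are about 0 to 5 per arm (largest: 29 × 0.20 × 0.9 = 5.22), so chance variation is also large.

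**The case against.** The strongest reply is that the protocol already knows the limitation and does not depend on serology for clinical infection. Adverse events are sought at every visit (10.1.1) and tabulated by treatment (SAP 7.2). Extra viral load or serology is allowed at the investigator's discretion (Table 8-1, footnote 10), and 8.2 allows extra samples if clinically indicated. 10.2.1 points to viral load for symptomatic subjects because serology may be diminished. CMV and EBV have scheduled PCR. All of this stands, and it limits the point to silent or unrecognised primary HSV infection.

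Three stronger readings are tempting, and the documents do not support them.

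- **That the trial's safety comparison as a whole will favour CFZ533.** The visible SAP text defines no seroconversion rate, infection endpoint or test. The summaries are descriptive, and adverse events and CMV/EBV PCR do not depend on HSV serology.
- **That SARS-CoV-2 surveillance has the same flaw.** On-treatment SARS-CoV-2 serum is saved rather than assayed at once (footnote 11, 8.3.2.5, 16.3.3), and PCR is described as possibly warranted for symptomatic subjects. The same bias arises only if the stored sera are later assayed and compared by arm.
- **That the drug switches the antibody signal off completely.** 10.2.1 says the response may be diminished. HSV serology includes IgM, and 4.5 describes normal or raised total IgM in CD154 deficiency, though with poor antibody function. The KLH result concerns one antigen and a transient effect. Near-total suppression is one end of the range.

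**Conclusion.** The point holds in a limited form. Between screening and one follow-up test, scheduled HSV monitoring is by antibody only, and the protocol itself expects CFZ533 to impair new antibody responses. Silent primary HSV infections in baseline-seronegative subjects may be under-detected on CFZ533 relative to placebo, and by-arm HSV serology summaries would then lean toward the drug. This rests on the protocol's own account of the pharmacology and on some seronegative subjects being enrolled and exposed. HSV incidence, the seronegative share and serology sensitivity by arm are not given, so the ratios of 0.56 and 0.22 are illustrations, not estimates. The on-treatment window adds to the problem: it removes from the summaries the one HSV result taken after washout, when a delayed antibody response could appear. The efficacy analysis is unaffected.

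**What to change.** 1. **Protocol 8.3.2.5 and 10.2.1 against 4.5 and 10.2.1.** Reconcile what HSV serology is said to show during treatment with the stated effect of CFZ533 on antibody responses. Whether and when to add viral load testing is for the sponsor and clinical team.
2. **SAP 7.** State that on-treatment HSV seroconversion, and SARS-CoV-2 seroconversion from any stored sera later assayed, is not interpreted as a comparative infection rate. Base the on-treatment infection comparison on reported infections and the viral load results available.
3. **SAP 7.1.** Add an exception to the on-treatment-only rule, so that follow-up HSV serology and viral load are summarised by arm against screening.

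The analysis changes cost SAP wording and one additional summary table. Items 2 and 3 need no new visit, sample or assay.

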8.3.2.6 Tanner staging (subjects 12 to 17 years only)

For subjects aged between 12 and 17 at visits as indicated in the Assessment Schedule, pubertal assessment will be carried out using the Tanner scale. While the details of the assessment will remain with the source document, the outcome of the evaluation (scale values 1 through 5) will be recorded in the eCRFs. Subjects who have reached sexual maturity, Tanner stage 5, do not need to have continued assessments.

8.3.3 ECG

A standard 12 lead ECG will be performed. Interpretation of the tracing must be made by a qualified physician and documented on the ECG section of the eCRF. Each ECG tracing should be labeled with the

- study number
- subject/ initials
- subject/ number
- date and kept in the source documents at the study site.

Only clinically significant abnormalities should be reported on this page. Clinically significant abnormalities should also be recorded on the relevant medical history/Current medical conditions eCRF page. Clinically significant findings must be discussed with the sponsor. Original ECG tracings, appropriately signed, will be archived at study site. The CRF will contain:

- date and time of ECG
- heart rate
- PR interval
- QT and QTcF interval
- RR interval
- QRS duration

8.3.4 Pregnancy

Females of child-bearing potential are defined as all females physiologically capable of becoming pregnant. This includes female pediatric subjects who are menarchal or who become menarchal during the study. Urine pregnancy test will be performed for all females of child-bearing potential according to the schedule in [Table 8-1](#). Serum pregnancy tests can be performed for positive urine tests and at the discretion of the site investigator. All menarchal girls and their guardian/caregiver should be informed about the potential risks of pregnancy and the need to prevent pregnancy during the study.

Pediatric subjects: In case of puberty and sexual activity, adolescents and when appropriate children will be informed about the need for preventing any pregnancy, testing for pregnancy and the management of the test results, including whether they will be shared with the guardian/caregiver. They should be counseled in a sensitive manner about abstinence (which should be promoted) and other forms of birth control. Their need, request and rights for privacy during the counseling process should be respected. Building a trusting relationship is important. These discussions with the subject and her guardian/caregiver are therefore best performed by investigators familiar with the pediatric subject and her family and should be guided by requirements of the local regulatory authorities. These discussions should take into account the socio-economic, cultural factors and religious beliefs of the adolescent participant and her family. The investigator should also discuss the management of the pregnancy test results with the subject and her guardian/caregiver. The privacy of the subject should be considered in accordance with the local law and ethics. Additional pregnancy tests may be performed at the

investigator's discretion during the study. Subjects becoming pregnant must be discontinued from study drug. However, a subject may choose to remain in the study should she become pregnant, and be followed according to the protocol-defined study visits.

Pharmacokinetic (PK) and pharmacodynamic (PD) studies show CFZ533 is cleared from the body and immune responses have normalized CCI post dose, and women are advised not to become pregnant until the PK/PD responses are eliminated. However, in the case that a subject becomes pregnant at any time during the trial, the pregnancy should be followed up to determine outcome, including spontaneous or voluntary termination, details of the birth, and the presence or absence of any birth defects, congenital abnormalities, or maternal and/or newborn complications to inform on fetal and early growth and developmental health. After consent is provided, the pregnancy reporting will occur up to one year after the estimated date of delivery or the pregnancy has ended in the absence of a live birth.

8.3.5 Appropriateness of safety measurements

The majority of safety assessments in this study are standard for this type of study (*i.e.*, AE monitoring, standard laboratory safety assessments, vital signs, ECGs and physical examinations).

Additional specific clinical laboratory assessments are included to exclude any active infection before treating the subject with study drug, which based on the pharmacology of CFZ533 could potentially put the subject at risk.

8.4 Additional assessments

Additional assessments are described below.

Commercially Confidential Information

Commercially Confidential Information

Commercially Confidential Information

Commercially Confidential Information

Commercially Confidential Information

9 Study discontinuation and completion

9.1 Discontinuation

9.1.1 Discontinuation of study treatment

Discontinuation of study treatment for a subject occurs when study treatment is stopped earlier than the protocol planned duration, and can be initiated by either the subject, the investigator, or the Sponsor.

The investigator must discontinue study treatment for a given subject if, he/she believes that continuation would negatively impact the subject's well-being.

Study treatment must be discontinued under the following circumstances:

- Subject/guardian decision
- Informed consent/assent is withdrawn
- Pregnancy
- Use of prohibited treatment as per recommendations in the prohibited treatment section (see [Section 6.2.2](#))
- Any situation in which study participation might result in a safety risk to the subject
- Following emergency unblinding

Subjects may voluntarily discontinue the study for any reason at any time.

Missing CCI will drop systemic drug levels below concentrations which can be expected to provide clinical efficacy. Subjects should therefore not miss more than 2 subsequent doses of study drug in CCI . Similarly, 2 consecutive doses cannot be missed more than once within a CCI period as this would also drop systemic levels below concentrations which can be expected to provide clinical efficacy. Subjects who have missed 3 or more doses in CCI or have missed 2 consecutive doses more than once within CCI will need to discontinue treatment permanently. The site should contact Novartis for further guidance if multiple compensatory doses are required.

Site Investigators should discontinue or temporarily suspend study treatment for any given subject if, on balance, they believe that continuation would be detrimental to the subject's well-being. Site Investigators should contact Novartis prior to resuming study drug that was discontinued or temporarily suspended for safety reasons. The DMC may be involved in the decision to resume dosing.

Study treatment must be discontinued and medical treatment must be started per standard of care where needed at the site Investigator's discretion under the following circumstances:

- Infusion reactions/anaphylaxis reactions to CFZ533.
- Recurrent systemic or severe infections. Recurrent local candidiasis, *e.g.* genital that is responsive to topical standard of care treatment and is deemed related to inadequate glycemic control is exempt.
- Severe infections. Resumption of dosing may be considered once the course of anti-infective therapy is completed and the infection is documented as cleared, so long as 3 or more doses have not been missed. For COVID-19, clearance of infection in order to resume treatment during the study requires resolution of symptoms and absence of infectious virus / viral replication from a respiratory specimen.
- Neutropenia with an absolute neutrophil count (ANC) $< 0.5 \times 10^9/L$ until resolution defined as an ANC $> 1 \times 10^9/L$ on 2 separate occasions.
- Severe and symptomatic hypogammaglobulinemia, *e.g.* IgG levels lower than 400 mg/dL necessitating replacement therapy with gamma globulins.

Resumption of dosing for subjects in whom study treatment was temporarily suspended must be decided based on the site Investigator's judgement, in consultation with the Sponsor and the DMC on a case-by case basis.

If permanent discontinuation of study treatment occurs, the investigator should make a reasonable effort to understand the primary reason for the subject's premature discontinuation of study treatment and record this information.

Subjects who discontinue study treatment or who decide they do not wish to participate in the study further should NOT be considered withdrawn from the study UNLESS they withdraw their consent/assent (see [Section 9.1.2](#) withdraw of informed consent section). Where possible, they should return for the assessments indicated in the assessment schedule. If they fail to return for these assessments for unknown reasons, every effort (*e.g.* telephone, e-mail, letter) should be made to contact the subject/pre-designated contact as specified in the lost to follow-up section (see [Section 9.1.3](#)). This contact should preferably be done according to the study visit schedule.

If the subject cannot or is unwilling to attend any visit(s), the site staff should maintain regular telephone contact with the subject, or with a person pre-designated by the subject. This telephone contact should preferably be done according to the study visit schedule.

After study treatment discontinuation, at a minimum, in abbreviated visits, the following data should be collected at clinic visits or via telephone/email contact:

- new / concomitant treatments
- Adverse Events/Serious Adverse Events

The investigator must also contact the IRT to register the subject's discontinuation from study treatment.

If discontinuation occurs because treatment code has been broken, please refer to Emergency breaking of treatment code section.

